A feasibility study undertaken by the chief investigator (CI), as part of a PhD programme of study, determined that an ankle placement of the Actigraph GT3X accelerometer was superior to the waist for determination of body position and step count. In this study, thirty healthy adult volunteers simulated patients weakened by critical illness. They performed a movement protocol which incorporated the typical activities undertaken by patients recovering in hospital from critical illness. These included moving from lying to sitting, sitting to standing (and vice versa) and walking short distances. Video recordings were taken of each participant during the movement protocols, enabling observation of the body positions adopted and step counting during the walking activities. Video recording was used as the criterion measure for comparison against the data captured by the accelerometers worn both at the ankle and the waist. The activities detailed above are typically included within early mobility protocols which have undergone evaluation within populations experiencing critical illness (McWilliams et al., 2015, Adler and Malone, 2012, Schweickert et al., 2009). Moderate agreement ($\kappa = 0.43$, $p < 0.001$), was found between observation of video recordings of body position (lying, sitting or standing) and the inclinometer setting for the ankle placement. Fair agreement only ($\kappa = 0.21$, $p < 0.001$) was found for the waist placement. Regular misclassification of all body positions was found with the waist placement. The ankle placement identified both the lying and standing positions well. The sitting position however was only correctly identified intermittently for the ankle placement. A novel finding emerged from this research relating to the ankle placement site. When a side lying position was adopted, the ankle accelerometer inclinometer function regularly registered a '0'. The '0' setting normally corresponds to a 'not being worn' option. When a reading of '0' was recoded to the option 'side lying,' agreement improved from $\kappa = 0.43$ ($p < 0.001$) to $\kappa = 0.48$ ($p < 0.001$). This finding suggests a new way of interpreting the '0' reading of the inclinometer when worn on the ankle, which is worthy of further investigation within an actual patient population.

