Participants will be free to undertake the activities within the semi-structured movement protocol in any order they prefer. Whilst undertaking the movements, participants will be observed by the CI. Although there is a requirement for the CI to be able to visualise them, the actual distance that she is from the patient will be determined according to the individual's wishes. Respect for privacy and dignity will be of paramount importance. Participants will not be observed if they are using a commode, the toilet or if bathing. The accelerometer data downloaded during these periods of time will be excluded from data analysis. A digital clock with an hour, minute and second display, successfully employed within the feasibility study will be used to note the time (to the hour, minute and second) when a particular movement or postural change occurred and ended. Once a postural change ends, a further five seconds will be observed on the digital clock before the new body position is documented as complete. This is to accommodate findings from the feasibility study and subsequent manufacturers recommendations related to how the accelerometer models process information. The digital clock will be synchronised to the time setting on a laptop computer, which will also be used to activate the desired settings on both accelerometers (termed 'initialisation'). These

processes will occur immediately before the data collection period to maximise synchronisation of the digital clock with the time setting on the accelerometers. The laptop computer will not be used during data collection, only for time synchronising the digital clock and for initialising the settings onto both accelerometers. The accelerometers will be programmed to capture data every second (one second epoch).

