Following completion of the data collection period, the information captured by the accelerometers will be downloaded as soon as possible onto the laptop computer. The time when a movement commenced and ceased (with the addition of five seconds to accommodate accelerometer processing), will be noted by the CI. The type of movement and body positions adopted will also be documented (lying, sitting or standing). If the movement involves walking, the CI will count the number of steps undertaken manually, entering all of the above information onto a data collection sheet. The participant will not miss any refreshments, food or any investigations and they will also be encouraged to undertake usual daily activities, e.g. reading a paper or watching the television. If the participant requests some time alone, in the case of making a phone call for example, the CI will comply, but encourage the participant to remain in the same body position. If they were sitting in a chair for example, they would be encouraged to remain seated, agreeing a time for the CI to return (e.g. fifteen minutes). Should any procedures or personal cares be necessary, the CI will respect the need for privacy and dignity and leave until they are complete. The data captured by the accelerometers during these time periods will be excluded from data analysis, as there will be no criterion measure (observation) to compare accelerometer data against.

Observational data will be collected by the CI using a data collection form specifically designed for this purpose, which will be entered into an electronic format within the IBM SPSS statistics programme (version 20) for data analysis. The CI will undertake all data collection procedures and undertake statistical analysis.

Upon completion of the period of observation the accelerometers will be removed and the skin examined for one final time. Participants will be asked to rate their views on acceptability of wearing the accelerometers at the two placement sites. They will be asked to consider the question in relation to the individual placement sites and in combination. One question will be asked:

1. How would you rate the comfort of wearing the accelerometers?

[figure not shown]
Participants will be requested to match their answer to a statement on a five-point Likert Scale which will be printed on a sheet for them:

1. Very uncomfortable
2. Somewhat uncomfortable
3. Neither comfortable or uncomfortable
4. Somewhat comfortable

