5. Very comfortable

A similar method of gaining feedback from participants regarding accelerometer comfort has been used in previous studies (Kramer et al., 2013).

Participants will also be asked if they have any comments they wish to make regarding the accelerometers, which will be noted as free text should any be forthcoming.

Study format

Semi structured movement protocol

1. Lying in bed with the legs straight and the bed head set at a comfortable height as dictated by the participant
2. Lying on the left side
3. Lying on the right side
4. Moving from lying to sitting over the side of the bed
5. Sitting to standing
6. Sitting in a chair
7. Mobilising a distance determined by the functional ability of the individual participant at that point in their recovery.

N.B. The participant will be free to undertake these movements in any order they wish, but there is a requirement to undertake as many of these movements as possible within the observation period, which will not exceed three hours. The participant will be provided with a sheet to remind them of the movements required to be undertaken. This will contain a tick box so they can mark off when a particular movement was completed. If a movement is missed, the CI will encourage the participant towards the end of the observation period to undertake it.

Infection control considerations

Advice has been sought from the HEYHT Infection Control Team regarding infection control considerations when using the accelerometers with patients' resident within HEYHT. The recommendations are as follows:

1. Elastics belts must be single patient use only and fastened using Velcro
2. The part of the accelerometer that permits download to the computer should be covered with a piece of easily removable tape (e.g. 'Scotchtape') to permit the whole device to be swabbed down with a Tristel wipe following the three-hour period of data collection per participant.
3. The devices are not required to be placed in a nylon pouch prior to application.

Tissue viability considerations

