A sample size of 20 participants will be recruited. This sample size has been used in previous research investigating the validity of a different accelerometer model to quantify gait parameters in patients recovering from critical illness (Edbrooke et al., 2012). They predicted that 12 subjects were necessary based upon alpha = 0.05 (significance level), beta = 0.9 (power) and a correlation of $r = 0.75$, categorised as a good to excellent correlation (Trapp and Dawson, 2004). A sample size of 20 was also recruited in another study investigating the validity of accelerometer measurement within a hospitalised stroke population (Kramer et al., 2013). Recruiting a sample of 20 patients will permit some attrition should there be any accelerometer malfunction or decisions to withdraw, yet supply an achievable number for participant recruitment based on feedback from clinical colleagues working within the specialty.

Statistical analysis

IBM SPSS statistics (Version 20) will be used to undertake statistical analysis. Some data captured by the accelerometers is continuous and others categorical.

Categorical data

Categorical data, concerning body position (lying, sitting or standing) will be analysed using the Kappa statistic, calculating agreement between the accelerometer inclinometer data and direct observation. Each accelerometer placement site (thigh and ankle) will initially be analysed separately. Examination of the inclinometer raw data captured from both placement sites will determine whether an algorithm can be constructed using readings from both the ankle and thigh placement to improve determination of the sitting

position specifically if necessary. Direct observation will serve as the criterion measure for all the analyses.

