Percentage agreement of inclinometer raw data from the thigh and ankle accelerometers with direct observation for detection of each separate body position will be calculated. A further percentage agreement analysis will be undertaken if an algorithm can be constructed for determination of the sitting position using readings from both placement sites. This algorithm will be compared against direct observational raw data identifying the sitting position only. This result will be compared against the percentage agreement of the individual placement sites in determination of the sitting position. This will assist in determination of whether the algorithm is more superior to a single placement site in determination of the sitting position.

Continuous data

Agreement between step count recorded by each accelerometer placement site and direct observation (manual counts) as a criterion measure will be determined using Bland Altman analysis with 95% limits of agreement (LOA).

Acceptance of the devices over a three-hour period

The statements within the Likert scale will be collapsed to obtain true positives (very comfortable and somewhat comfortable) and true negatives (very uncomfortable and somewhat uncomfortable). The middle category (neither comfortable nor uncomfortable) will remain a separate category. A descriptive analysis will be undertaken to investigate this particular aspect of enquiry using percentages of true positives, the middle category and true negatives. This will be presented graphically.

Any specific comments made by the patients in relation to acceptability of the devices will be included as free text within the results section. The statements will be anonymous and permission from participants will be sought regarding their inclusion within the body of the thesis or publications which may arise from it.

Ethics approval

This study has received approval from the NHS Local Research Ethics Committee (REF: XXXXX) and the Research Ethics Sub Committee, YSJU (REF: XXXXXX).

Data handling and confidentiality

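### Agreement is planned only for lying, sitting and standing, so poor agreement in a briefly held scripted posture, notably side lying at the ankle, can be diluted within its class

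*Combined protocol and SAP*

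**What the plan says.** All references are to the combined protocol and SAP.

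- **Postures scripted.** Study format (Semi structured movement protocol) lists lying with the legs straight, "Lying on the left side", "Lying on the right side", a move to sitting over the bed edge, and chair sitting as separate items. Order is free and no time is set for any of them.
- **What is recorded.** Study procedure: "The type of movement and body positions adopted will also be documented (lying, sitting or standing"). The same section states: "The accelerometers will be programmed to capture data every second (one second epoch").
- **What is analysed.** Statistical analysis (Categorical data): "Categorical data, concerning body position (lying, sitting or standing) will be analysed using the Kappa statistic". Then, percentage agreement of the raw inclinometer readings at each site "with direct observation for detection of each separate body position will be calculated". Neither sentence names a unit of analysis (second, bout or participant), and the section mentions neither side lying nor device code 0.
- **What was already seen.** The account of the feasibility study in the background reports: "When a side lying position was adopted, the ankle accelerometer inclinometer function regularly registered" a 0. Recoding 0 as side lying moved kappa from 0.43 to 0.48, and the finding is put forward for further study in patients. Data collection process still defines 0 as a device that is off or not worn.

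**The concern.** Reporting each class separately stops sitting from hiding lying, but it does nothing inside a class. If one-second readings are pooled, each posture counts in proportion to the time spent in it. Participants choose where they rest, so the lying figure may come mostly from their preferred resting position.

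Hypothesis 1 says the ankle device will identify lying accurately. Two groups with the same device performance in each posture could give quite different answers. The study also collects the patient data needed to test its own side-lying observation, but plans no analysis that would report the result. Sitting could mix in the same way, and that bears on the sitting algorithm of Objective 3 and Hypothesis 3.

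**Working it through.** The documents give no agreement rate by posture and no time per posture, so there is no planned figure to reproduce. The rates and minutes below are assumptions, chosen to show the range.

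**Formula.** If readings are pooled over time, agreement for a class is the sum of (minutes in posture × agreement in posture) divided by total minutes in the class.

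**1. Lying, imperfect agreement in both postures.** Assume 98% supine and 10% in side lying.

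- 40 min supine, 4 min side lying: (40 × 0.98 + 4 × 0.10) / 44 = 39.6 / 44 = 90%.
- 40 min supine, 40 min side lying: (40 × 0.98 + 40 × 0.10) / 80 = 43.2 / 80 = 54%.

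Only the resting time differs between the two.

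**2. Lying, by treatment of code 0.** Assume supine is always read correctly and side lying always reads 0. This is an extreme case; the feasibility account says regularly.

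| Supine / side lying (min) | 0 counted as disagreement | 0 dropped as not worn | 0 recoded as side lying |
|---|---|---|---|
| 60 / 2 | 60/62 = 96.8% | 100% | 100% |
| 60 / 4 | 60/64 = 93.8% | 100% | 100% |
| 60 / 10 | 60/70 = 85.7% | 100% | 100% |
| 45 / 20 | 45/65 = 69.2% | 100% | 100% |
| 30 / 30 | 30/60 = 50.0% | 100% | 100% |

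Complete failure in side lying is almost invisible when the posture is brief and obvious when it lasts as long as supine. If 0 is dropped, it leaves no trace at all. Dropping and recoding give the same lying percentage here but mean different things: one discards the side-lying seconds, the other counts them as correct.

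**3. Kappa.** Minutes are in the order supine / side lying / chair / bed edge / standing. Code 0 is kept as a separate category. This step also assumes, purely for illustration, that bed-edge sitting always reads as standing.

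- 60/4/90/3/10 (167 min): observed agreement 160/167 = 0.958; chance agreement (64 × 60 + 93 × 90 + 10 × 13) / 167² = 0.442; kappa = 0.925.
- 30/30/60/30/20 (170 min): observed agreement 110/170 = 0.647; chance agreement (60 × 30 + 90 × 60 + 20 × 50) / 170² = 0.284; kappa = 0.507.

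Both totals fit within the three-hour limit.

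**4. Sitting, hypothetical.** Assume 95% in a chair for 60 min and 20% at the bed edge for 1 min: (60 × 0.95 + 1 × 0.20) / 61 = 57.2 / 61 = 93.8%. That is 1.2 points below the chair figure alone.

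**The case against.** The case for the plan has real force.

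- **The weighting is not written.** The one-second epoch is a capture setting. A reader might infer that the plan weights by seconds, but it names no unit of analysis. This stands. The gap is the silence, together with the most natural reading of agreement on raw data.
- **Durations are unknown.** A reader might infer that long supine and chair periods will swallow the other postures. The documents do not give those times, and the range above runs from negligible to large. Dilution can happen; it is not shown to happen.
- **Side lying depends on code 0.** It would be tempting to say the problem is the same however code 0 is scored. It is not: the only documented difference within a class is the 0 reading, and recoding it may remove most of that difference. The feasibility account also says lying was identified well overall and that 0 was regular, not invariable.
- **Bed edge.** Nothing in the documents shows bed-edge and chair sitting reading differently. The feasibility account says only that sitting was intermittently identified at the ankle, and the scripted item is worded as a transfer. This part is hypothetical.
- **Three classes suit the device and the question.** The inclinometer has one lying code and one sitting code. For monitoring in naturalistic conditions, time weighting is defensible. This supports keeping the three-class figures, but does not supply the missing breakdown.
- **Posture may be recoverable.** Type of movement is recorded, with times to the second. That lowers the cost of the fix; it does not put the analysis in the plan.

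**Conclusion.** The concern holds in a limited form. The plan scripts five lying and sitting postures, analyses them as two classes, states no unit of analysis and sets no time per posture. Poor agreement in a briefly held posture can therefore be diluted, and the lying figure for Hypothesis 1 can depend on resting preference. In the assumed cases, lying agreement for an unchanged device runs from 96.8% to 50.0% when code 0 counts as disagreement, and is 100% when code 0 is dropped or recoded. Those sizes rest on pooling by time and on assumed minutes and rates.

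The firm part is side lying at the ankle: it was observed in the feasibility study, is worth testing by the protocol's own account, is scripted, and then has no analysis.

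A reader might go further and conclude that Hypothesis 1 will be decided by resting preference alone, or that the device fails at the bed edge. The documents support neither: Hypothesis 1 has no acceptance threshold, and no bed-edge result is reported.

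**What to change.** - **Study procedure and Data collection process.** Code the observed posture on the data sheet (supine, left side, right side, bed edge, chair, standing, walking) and note which leg carries the sensors.
- **Statistical analysis (Categorical data).** State the unit of analysis. Keep the three-class figures. Add percentage agreement by posture, calculated per participant and then summarised, with the time spent in each posture.
- **Code 0.** Show side lying twice: with 0 as recorded, counted as disagreement and not dropped, and with 0 recoded as side lying.
- **Conclusions.** Limit those on Hypothesis 1 and the sitting algorithm to the postures in which agreement is shown.

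A composite with equal weight per posture is not recommended. It would give the two side-lying items two-thirds of the lying figure, and it would be undefined for a participant who misses a posture, which the protocol allows.

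The cost is one extra code and a longer results table. With 20 participants, figures for briefly held postures will be imprecise and should be presented as such.

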3. To investigate the criterion validity of the combination of thigh and ankle accelerometer inclinometer outputs to correctly determine the sitting position. This

will determine whether an algorithm can be constructed using the two inclinometer readings, which will better distinguish the sitting from the standing position.

4. To evaluate, from a user perspective, the acceptability of these devices in relation to the placement sites used. This will be achieved by asking patients to score the answer to a particular question through the use of a Likert scale. The question is:
 - How would you rate the comfort of wearing the accelerometers?

In consideration of the results from the feasibility study undertaken by the CI and research using the addition of a thigh mounted accelerometer to identify the sitting position (Skotte et al., 2014), the following hypotheses can be constructed:

Hypotheses

1. An ankle mounted Actigraph GT3X accelerometer, will accurately identify both the lying and standing positions when compared with direct observation as a criterion measure.
2. An ankle mounted Actigraph GT3X accelerometer, will capture a step count comparable to that recorded by direct observation in a population resident on a hospital ward recovering from critical illness.
3. The combination of inclinometer outputs of both the thigh and ankle placement sites will permit development of an algorithm permitting the ability to better distinguish between the sitting and standing position.
4. The ankle and mid-thigh accelerometer placement sites will be well tolerated by patients recovering on a ward from critical illness.

Subject selection and involvement

The study will invite adult hospital ward patients recovering from critical illness to wear one Actigraph GT3X accelerometer on the antero-medial mid-thigh and another on the ankle, resting above the lateral malleolus of the same leg. The accelerometers will be worn for a period of time not exceeding three hours. Each device will be attached with a single patient use broad elastic belt, secured by Velcro fastening, using a standardised placement protocol. The non – dominant leg will be the preferred placement side.

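### The combined thigh-ankle analysis rests on two undefined judgements made on the study's own data, so Objective 3 may end without a figure

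*Combined protocol and SAP*

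**What the plan says.** Objective 3 in the combined protocol and SAP is "To investigate the criterion validity of the combination of thigh and ankle accelerometer inclinometer outputs" for the sitting position. Its second sentence adds that this work "will determine whether an algorithm can be constructed using the two inclinometer readings". Hypothesis 3 states that the combined outputs "will permit development of an algorithm permitting the ability to better distinguish between the sitting and standing position".

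Statistical analysis, Categorical data, treats the single sites and the combination differently:

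- Single sites: "Percentage agreement of inclinometer raw data from the thigh and ankle accelerometers with direct observation for detection of each separate body position will be calculated". No condition is attached.
- Building the algorithm: "Examination of the inclinometer raw data captured from both placement sites will determine whether an algorithm can be constructed", with the aim of improving determination of the sitting "position specifically if necessary".
- Analysing the algorithm: "A further percentage agreement analysis will be undertaken if an algorithm can be constructed". If there is one, it is scored against observed sitting only and compared with each single site.

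The plan does not say what makes an algorithm necessary, or what counts as having constructed one. Under Study procedure, the same investigator collects all the data, including the reference observations, and carries out the statistical analysis.

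**The concern.** The objective asks how valid the combination is. The plan answers with a figure only if two judgements, both made after seeing the data, go a particular way. Only the two-site result is optional in this sense.

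Two consequences follow. First, a reader may learn that no algorithm was needed, or that none could be built, without any two-site agreement from which to check that conclusion. Second, a two-site figure that does appear will belong to a rule chosen by inspecting the participants on whom it is then scored. Cross-validation alone would not cure the first problem, because the decision whether to do the analysis at all comes before it.

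**Working it through.** The plan gives no figure for this analysis. Its one calculation, 12 subjects for r = 0.75, is borrowed from another study and concerns a correlation. The check is therefore mainly of the text.

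**1. Follow each route through the plan.**

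| Route | Two-site figure reported? | What it says about Hypothesis 3 |
|---|---|---|
| (a) Algorithm judged not necessary | No | Untested |
| (b) Algorithm judged not constructible | No | Contradicted, in words only |
| (c) Algorithm built, no better than a single site | Yes | Counts against it |
| (d) Algorithm built, better than a single site | Yes | Supports it, on the data used to choose the rule |

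Routes (a) and (b) leave Objective 3 without a number. Nothing in the plan determines which route is taken.

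**2. Is constructibility a fact or a judgement?** Data collection process lists four inclinometer codes (0, 1, 2, 3) per device.

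- Thigh-ankle code pairs: 4 × 4 = 16.
- Possible sit/not-sit rules over those pairs: 2^16 = 65,536.

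Some rule can always be written down, so whether one can be constructed is a judgement about whether it seems useful.

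**3. Was the need foreseeable?** The background reports that in the feasibility study the ankle device identified sitting only intermittently, and the thigh site was added with that in mind. The question of need could have been settled before data collection.

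**4. How much protection does route (c) give?** Less than it appears to, for two reasons.

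*Scoring on sitting only.* A rule that calls sitting when either site reads sitting can never score below the better single site on observed sitting. As an illustration, assume independent sites, with ankle agreement a of 0.3 to 0.7 and thigh agreement t of 0.5 to 0.9:

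- Either-site rule, 1 − (1 − a)(1 − t): from 1 − 0.7 × 0.5 = 0.65 to 1 − 0.3 × 0.1 = 0.97.
- Both-sites rule, a × t: from 0.3 × 0.5 = 0.15 to 0.7 × 0.9 = 0.63.

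The choice of rule therefore largely fixes whether the combination can look worse.

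*Scoring on the building data.* An illustrative simulation used 2,000 runs of 20 participants, each with one sitting and one standing bout. The ankle read sitting in 50% of sitting and 10% of standing bouts, the thigh reading was pure noise, and a majority rule was applied in each code-pair cell. Accuracy was over both postures, compared with the ankle alone. On the building data the mean gain was +3.3 points, above zero in 58% of runs and never below zero. On new data the mean was −4.0 points. These inputs are assumptions; the run shows the direction of the problem and does not estimate its size in this study.

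**The case against.** The strongest reply is that constructibility is itself a declared output. Objective 3 sets out to learn whether an algorithm can be built, and Hypothesis 3 predicts that it can. A report that none could be built answers the objective and contradicts the hypothesis. If one is built, the comparison with each site can go either way, and no text suppresses an unfavourable one. Single-site sitting figures are always available. This is also a descriptive study of 20 patients with no planned test of superiority.

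Much of that stands, and it rules out three stronger readings that a reader might reach:

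- *That Hypothesis 3 can be supported but never refuted, or that a null result always goes unreported.* Routes (b) and (c) both count against the hypothesis, and route (c) gives a figure.
- *That the reported gain is inflated by a calculable amount because only positive gains are published.* The plan contains no rule to report only if positive, and it gives no variance for a paired difference.
- *That Objective 3 is the sole reason for the second device.* Objectives 1 and 2 need both sites, and Objective 4 asks about comfort at the sites used.

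The reply does not remove the gap itself. Route (a) leaves the hypothesis untested, route (b) gives a negative with no number and no standard behind it, and routes (c) and (d) score a rule on the data that suggested it. The always-reported single-site figures do not show what the combination would have achieved.

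**Conclusion.** The point holds in this form: the two-site analysis for Objective 3 is conditional on two undefined judgements made from the study's own data, so it may be left undone or given without a figure. Any figure that is given belongs to a rule chosen on the same participants. The plan also sets no standard for deciding that the combination has failed.

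No magnitude in percentage points can be taken from the documents. The extent is that one of the four objectives may lack its quantitative answer while the single-site results are always shown. This conclusion rests on the wording and on the count of 16 code pairs; it does not depend on the illustrative figures. The change should be made, since it is cheap and uses data that will be collected anyway.

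**What to change.** Under Statistical analysis, Categorical data:

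1. Delete both conditions, the one on need and the one on constructibility.
2. Always report, for all participants with data, the table of the 16 thigh-ankle code pairs against observed posture.
3. Before data collection, fix one rule stating which code pairs count as sitting, including pairs with a 0 reading. Always report its agreement with observed sitting beside that of each single site, whatever the result.
4. State that a fixed rule no better than the better single site counts against Hypothesis 3. Because an either-site rule cannot lose on sitting alone, show beside it the share of observed standing that the rule calls sitting; the table in step 2 supplies this.
5. Report any rule found by inspection in addition, labelled exploratory.

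The cost is a few sentences of wording and one more table, with no extra patients or measurements. There are two real downsides. The rule must be chosen without thigh-ankle data from the study team, whose feasibility study used the ankle and waist, so the first choice may be a poor one; step 5 keeps the route to a better rule open. The study may also have to show an unflattering two-site figure.
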